2.5 Safety Endpoints

The safety endpoints include the following:

- BDCVA (normal and low luminance) at 4 m
- Slit-lamp biomicroscopy
- Conjunctival redness grading
- Study drug drop comfort assessment
- IOP
- Dilated indirect fundoscopy
- AEs (reported, elicited, and observed)

2.6 Statistical Hypotheses

The primary efficacy hypothesis is:

H_{01} : The difference between study eyes treated with CSF-1 and study eyes treated with Vehicle, in the percentage of study eyes with a ≥ 3 -line (15-letter) improvement from baseline in BDCVA at 40 cm (Precision Vision chart) without a loss in BDCVA of ≥ 5 letters (ETDRS at 4 m) at Visit 3 (Day 8), 1 hour post-dose 1 = 0

H_{11} : The difference between study eyes treated with CSF-1 and study eyes treated with Vehicle, in the percentage of study eyes with a ≥ 3 -line (15-letter) improvement from baseline in BDCVA at 40 cm (Precision Vision chart) without a loss in BDCVA of ≥ 5 letters (ETDRS at 4 m) at Visit 3 (Day 8), 1 hour post-dose 1 $\neq 0$

The study will be considered a success if the null hypothesis, H_{01} , is rejected at a 2-sided alpha = 0.05 in favor of CSF-1 in the alternative hypothesis, H_{11} , tested as delineated in the primary efficacy analysis section, and the following secondary efficacy hypotheses will each be tested as stated under adjustments for multiplicity.

The key secondary efficacy hypotheses are:

Visit 3 (Day 8)

Visit 3, 2 Hours Post-Dose 1

H_{02} : The difference between study eyes treated with CSF-1 and study eyes treated with Vehicle, in the percentage of study eyes with a ≥ 3 -line (15-letter) improvement from baseline in BDCVA at 40 cm (Precision Vision chart) without a loss in BDCVA of ≥ 5 letters (ETDRS at 4 m) at Visit 3 (Day 8), 2 hours post-dose 1 = 0.

H_{12} : The difference between study eyes treated with CSF-1 and study eyes treated with Vehicle, in the percentage of study eyes with a ≥ 3 -line (15-letter) improvement from baseline in BDCVA at 40 cm (Precision Vision chart) without a loss in BDCVA of ≥ 5 letters (ETDRS at 4 m) at Visit 3 (Day 8), 2 hours post-dose 1 \neq 0.

Visit 3, 1 Hour Post-Dose 2

[figure not shown]
H_{03} : The difference between study eyes treated with CSF-1 and study eyes treated with Vehicle, in the percentage of study eyes with a ≥ 3 -line (15-letter) improvement from baseline in BDCVA at 40 cm (Precision Vision chart) without a loss in BDCVA of ≥ 5 letters (ETDRS at 4 m) at Visit 3 (Day 8), 1 hour post-dose 2 = 0.

H_{13} : The difference between study eyes treated with CSF-1 and study eyes treated with Vehicle, in the percentage of study eyes with a ≥ 3 -line (15-letter) improvement from baseline in BDCVA at 40 cm (Precision Vision chart) without a loss in BDCVA of ≥ 5 letters (ETDRS at 4 m) at Visit 3 (Day 8), 1 hour post-dose 2 \neq 0.

Visit 3, 2 Hours Post-Dose 2

H_{04} : The difference between study eyes treated with CSF-1 and study eyes treated with Vehicle, in the percentage of study eyes with a ≥ 3 -line (15-letter) improvement from baseline in BDCVA at 40 cm (Precision Vision chart) without a loss in BDCVA of ≥ 5 letters (ETDRS at 4 m) at Visit 3 (Day 8), 2 hours post-dose 2 = 0.

[figure not shown]
H_{14} : The difference between study eyes treated with CSF-1 and study eyes treated with Vehicle, in the percentage of study eyes with a ≥ 3 -line (15-letter) improvement from baseline in BDCVA at 40 cm (Precision Vision chart) without a loss in BDCVA of ≥ 5 letters (ETDRS at 4 m) at Visit 3 (Day 8), 2 hours post-dose 2 \neq 0.

[figure not shown]

[figure not shown]

[figure not shown]

[figure not shown]

3. Study Design and Procedures

3.1 Overall Study Design

This is a four-visit multi-center, randomized, double-masked, parallel-group study evaluating the safety and efficacy of CSF-1 compared with Vehicle in approximately 300 subjects with presbyopia. The study design is summarized in Figure 1.

Visit 1 (Screening, Day -14 to -1): Qualified subjects will receive 1 drop of Vehicle instilled in each eye, followed by preliminary efficacy assessments to identify Vehicle responders at 15 minutes post-vehicle instillation.

Vehicle responder is defined as a subject who had a > 0.14 LogMAR (i.e., 7 letters) improvement in post-Vehicle treatment (at 15 minutes post-Vehicle treatment) monocular BDCVA in either eye at 40 cm

compared to Visit 1 pre-treatment, or a > 0.14 LogMAR (i.e., 7 letters) improvement in monocular BDCVA in either eye at 40 cm between Visit 1 (pre-treatment) and Visit 2 (pre-treatment baseline).

Visit 2 (Day 1): Baseline assessments. Subjects who meet all inclusion and none of the exclusion criteria and qualify as Vehicle non-responders, will be randomized 1:1 to one of the following treatment arms:

- CSF-1 (0.4% pilocarpine hydrochloride ophthalmic solution)
- Vehicle

Pre-treatment measurements taken at this visit are considered as baseline.

[figure not shown]
At the Visit 2 (Day 1) clinic visit, study personnel will instill Dose 1 of study drug at 8:30 AM \pm 30 minutes in each eye. Efficacy and safety assessments will be conducted for 2 hours following Dose 1. Dose 2 will be instilled by study personnel at 10:30 AM \pm 30 minutes in each eye. Efficacy and safety assessments will be conducted for 4 hours following Dose 2.

All subjects will be instructed to dose twice daily (BID) with a single drop in each eye for approximately 1 week. The first daily dose should occur in the morning, with the second dose following 2 hours later (± 1 hour). Subjects will be instructed not to dose at home on clinic visit days.

Visit 3 (Day 8): Study personnel will instill Dose 1 of study drug at 8:30 AM \pm 30 minutes in each eye. Efficacy and safety assessments will be conducted for 2 hours following Dose 1. Dose 2 will be instilled by study personnel at 10:30 AM \pm 30 minutes in each eye. Efficacy and safety assessments will be conducted for 2 hours following Dose 2.

[figure not shown]
All subjects will be instructed to dose twice daily (BID) with a single drop in each eye, for approximately 1 week. The first daily dose should occur in the morning with the second dose following 3 hours later (± 1 hour). Subjects will be instructed not to dose at home on clinic visit days.

[figure not shown]
Visit 4 (Day 15): Study personnel will instill Dose 1 of study drug at 8:30 AM \pm 30 minutes in each eye. Efficacy and safety assessments will be conducted up to 3 hours following Dose 1. Dose 2 will be instilled by study personnel at 11:30 AM \pm 30 minutes in each eye. Efficacy and safety assessments will be conducted for 5 hours following Dose 2.

[figure not shown]
Figure 1. Study Design

3.2 Schedule of Visits and Measurements

Table 1 Schedule of Visits and Assessments

4. Study Treatments

The investigational product (IP) is CSF-1, a sterile topical eye drop solution. The formulation developed by Orasis Pharmaceuticals Ltd. is a preservative-free eye drop, containing the active ingredient pilocarpine hydrochloride 0.4%, with the addition of standard pharmacopoeial excipients used in sterile ophthalmic solutions.

The vehicle (CSF-1 placebo) is a topical eye drop solution containing the same ingredients as in CSF-1 except for the active ingredient.

Both IP and Vehicle are packaged in a single-dose transparent low-density polyethylene (LDPE) vials, enclosed within a pouch. Each pouch includes five vials. Kits will be dispensed to subjects at Visit 2 (Day 1) and Visit 3 (Day 8) with 1 week of at-home dosing in each kit. CSF-1 will be evaluated for comparison to Vehicle.

Following the pre-treatment assessments, qualified subjects will be randomized to 1:1 to one of the following treatment arms:

1. CSF-1: Pilocarpine Hydrochloride (0.4%) Ophthalmic Solution
2. Placebo (Vehicle)

After randomization at Visit 2 (Day 1), subjects will receive study drug and a paper dosing diary. Each subject will instill one drop of study drug to each eye and keep aside the used vial to be returned to the site

at next visit for compliance check. Following Visit 2, subjects will be instructed to dose bilaterally BID (with 2 hours (+1 hour) between doses) and record doses in their diary until Visit 3. Subjects should not dose at home on day of Visit 3. Following Visit 3, after subjects receive their study drug and dosing diary, subjects will be instructed to dose bilaterally BID (with 3 hours (+1 hour) between doses) and record doses in their diary until Visit 4. Subjects should not dose at home on day of Visit 4. At Visit 4, subjects will receive their doses at the visit by study personnel after the required pre-treatment assessments and their study drug will be collected. Subjects will exit the study after all assessments are complete at Visit 4.

4.1 Method of Assigning Subjects to Treatment Groups

Each subject who signs an informed consent form (ICF) will be assigned a subject number. Subject numbers will be assigned in sequential order beginning with 001. Once a subject meets all qualification criteria at Visit 2 (Day 1), they will be randomized in a 1:1 ratio via an Interactive Response Technology (IRT) system to one of the following treatment groups: (1) CSF-1 or (2) Vehicle, and stratified by iris color (brown versus light [i.e., blue, green, gray, and hazel]) and by baseline manifest refraction spherical equivalent <-0.5 D, -0.5 D to +0.75 D, and >+0.75 D); randomization will not be stratified by site.

At least, approximately, 30% of subjects will have a light iris and at least, approximately, 30% will have a brown iris. The actual percentages will vary based on enrollment.

Randomization will be used to avoid bias in the assignment of subjects to treatment, to increase the likelihood that known and unknown subject attributes (e.g., iris color and baseline characteristics) are evenly balanced across treatment groups, and to enhance the validity of statistical comparisons across treatment groups. Double-masked treatment will be used to reduce the potential of bias during data collection and the evaluation of clinical endpoints.

4.2 Masking and Unmasking

An independent, unmasked biostatistician who is not otherwise involved in the trial will generate the complete randomized study drug kit list. The subject, study sponsor, medical investigators, and study staff will be masked during the entire randomization process and throughout the course of the study. When medically necessary, the investigator may need to determine what treatment has been assigned to a particular subject. When possible (i.e., in non-emergent situations), [REDACTED] and/or the study sponsor should be notified before unmasking the IP. In emergency situations, the investigator must notify the sponsor within 24 hours after determining that it is necessary to unmask the treatment assignment. The investigator must also indicate in source documents and in the electronic case report form (eCRF) that the mask was broken and provide the date, time, and reason for breaking the mask.

5. Sample Size and Power Considerations

A total sample size of 280 subjects (140 subjects per arm) yields > 97.5% power to establish superiority of CSF-1 to Vehicle in the percentage of study eyes demonstrating a \geq 3-line (15-letter) gain from baseline in BDCVA at 40 cm (Precision Vision chart) and no loss of BDCVA \geq 5 letters (ETDRS at 4 m), 1-hour post

each dose on Visit 3 (Day 8) assuming a response rate of 42.5% in CSF-1 and 17.5% in Vehicle using a Pearson chi-squared test with a 2-sided significance level of 0.05.

A series of horizontal black bars of varying lengths, likely representing redacted text or data. The bars are arranged vertically and span the width of the page. Some bars are longer, while others are shorter, indicating different lengths of redacted content.

Accounting for approximately a 5% discontinuation rate, approximately 150 subjects per arm (approximately 300 total) will be randomized.

6. Data Preparation

All reported study data will be recorded on the eCRFs supplied by Statistics & Data Corporation (SDC) using iMedNet™. Only the Principal Investigator and authorized study staff according to the Delegation of Responsibilities log are entitled to make entries in the eCRF. After data are entered into the clinical study database, electronic edit checks, and data review will be performed. All data validation specifications and procedures are detailed in the Data Validation Manual as a separate document. When the database has been declared to be complete and accurate, the database will be locked. Any changes to the database after data have been locked can only be made with the approval of the sponsor and [REDACTED] in consultation with SDC.

The final analyses outlined in this document will be carried out only after the following have occurred:

- All data management requirements are met according to SDC standard operating procedures, including data entry, performance of edit and validation checks, documentation and resolution of data queries, and database lock with written authorization provided by appropriate SDC and sponsor personnel.

- Protocol deviations have been identified and status defined (major/minor deviations), and completed prior to database lock and study unmasking.
- Analysis populations have been determined, and completed prior to database lock and study unmasking.
- Randomized treatment codes have been unmasked.

7. Analysis Sets

7.1 Full Analysis Set

The full analysis set (FAS) will include all randomized subjects who have received at least one dose of the study drug. Subjects in the FAS will be analyzed as randomized. The FAS analysis set will be the primary analysis set for the determination of efficacy.

7.2 Per Protocol Set

The per-protocol set (PPS) will include subjects in the FAS who do not have significant protocol deviations that affect the primary efficacy endpoint analyses. Protocol deviations will be assessed prior to database lock and unmasking. Subjects in the PPS will be analyzed as treated. The PPS analysis will be supportive of the primary and key secondary efficacy analysis performed with FAS.

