Descriptive statistics will be presented by treatment group. Testing of the percentage of subjects with at least a 3-line (15-letter) improvement from baseline in BDCVA at 40 cm without a loss of  $\geq 5$  letters in best distance corrected VA at 4m will be completed separately for the 1 hour and 2 hour time points using a generalized linear mixed model with a binomial distribution including fixed effects of baseline BDCVA at 40 cm as a covariate, daily dose (Dose 1 and Dose 2), treatment, and the interaction of dose with treatment and random effect of subject to account for the correlation within a subject between daily doses. The dose-by-treatment interaction term will be used to check if there is differential treatment effect between Dose 1 and Dose 2. If the dose-by-

treatment interaction term is significant ( $p < 0.10$ ), then the interaction term will remain in the model and testing of the treatment effect will be completed within the model separately following Dose 1 and following Dose 2. If the dose-by-treatment interaction term is not significant ( $p \geq 0.10$ ), then the interaction term will be removed from the model and testing of treatment effect will be completed within the model pooled over dose.

The adjusted odds ratios and marginal proportions and difference in proportions along with corresponding two-sided 95% Confidence Intervals (CIs) and p-values will be presented.

Treatment comparisons will also be made separately for each time point and dose using logistic regression model including fixed effects of baseline BDCVA at 40 cm as a covariate and treatment, Pearson's chi-squared test or Fisher's exact test if any of the cell counts are less than five as a sensitivity analysis to the primary model above.

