### 10.3 Study Populations

- Full Analysis Set – The full analysis set (FAS) will include all randomized subjects who have received at least one dose of the study drug. Subjects in the FAS will be analyzed as randomized.
- Per Protocol Set – The per-protocol (PP) set will include subjects in the FAS who do not have significant protocol deviations that affect the primary endpoint analysis. Protocol deviations will be assessed prior to database lock and unmasking. Subjects in the PP set will be analyzed as treated.
- Safety Set – The safety set will include all subjects who have received at least one dose of the study drug. Subjects in the safety population will be analyzed as treated.

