### 10.7 Efficacy Analysis

#### Primary Efficacy Analyses

The primary efficacy endpoint in this study is the percentage of subjects with a  $\geq 3$ -line (15-letter) gain, from baseline, in best distance-corrected visual acuity (BDCVA) at 40 cm (Precision Vision chart) and no loss in best distance corrected visual acuity  $\geq 5$  letters (ETDRS chart) at Visit 3, 1 hour following Dose 1 in the study eye. The primary efficacy analysis will be conducted in the FAS with intercurrent events handled in the following manners:

- 1) Discontinuation of study drug and non-optimal compliance will be ignored [treatment policy strategy].
- 2) Withdrawal due to lack of efficacy or adverse events: missing data will be singly imputed as failure [hypothetical strategy].
- 3) Missing data without withdrawal or withdrawal due to reasons other than lack of efficacy or adverse events: missing data will be imputed employing Multiple Imputation (MI) using randomized treatment-based Markov Chain Monte Carlo (MCMC) methodology [hypothetical strategy].

No subject data will be excluded from the FAS due to protocol violations/deviations. The FAS will be used for the primary efficacy analyses. Note that multiple imputations of missing values will be completed for the continuous measures (BDCVA at 40 cm and best distance corrected VA at 4m), then the response variable will be determined therefrom.

[REDACTED]

Descriptive statistics will be presented by treatment group. Testing of the percentage of subjects with at least a 3-line (15-letter) improvement from baseline in BDCVA at 40 cm without a loss of  $\geq 5$  letters in best distance corrected VA at 4m will be completed separately for the 1 hour and 2 hour time points using a generalized linear mixed model with a binomial distribution including fixed effects of baseline BDCVA at 40 cm as a covariate, daily dose (Dose 1 and Dose 2), treatment, and the interaction of dose with treatment and random effect of subject to account for the correlation within a subject between daily doses. [REDACTED]

[REDACTED]

The adjusted odds ratios and marginal proportions and difference in proportions along with corresponding two-sided 95% Confidence Intervals (CIs) and p-values will be presented.

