List of Figures:

Figure 1. Study Design.....	17
-----------------------------	----

List of Abbreviations

AE	Adverse Event
ATC	Anatomical Therapeutic Chemical
BCVA	Best Corrected Visual Acuity
BDCVA	Best Distance-Corrected Visual Acuity
BID	Twice Daily
CI	Confidence Interval
eCRF	Electronic Case Report Form
ETDRS	Early Treatment of Diabetic Retinopathy Study
FAS	Full Analysis Set
GEE	Generalized Estimating Equation
ICF	Informed Consent Form
ICH	International Council for Harmonisation
IMDF	Imputing Missing Data as Failures
IOP	Intraocular Pressure
IP	Investigational Product
IRT	Interactive Response Technology
HIPAA	Health Information Portability and Accountability Act
LDPE	Low-Density Polyethylene
LL-BDCVA	Low-Luminance Best Distance-Corrected Visual Acuity
logMAR	Logarithm of the Minimum Angle of Resolution
LS	Least Square
MCMC	Markov Chain Monte Carlo
MedDRA	Medical Dictionary for Regulatory Activities
MI	Multiple Imputation
NCS	Not Clinically Significant
ODO	Observed Data Only
PPS	Per Protocol Set
PT	Preferred Term
SAE	Serious Adverse Event
SAF	Safety Set
SAP	Statistical Analysis Plan
SD	Standard Deviation
SDC	Statistics & Data Corporation
SOC	System Organ Class
TEAE	Treatment-Emergent Adverse Event
TPA	Tipping Point Analysis
VA	Visual Acuity
WHO	World Health Organization

1. Introduction

The purpose of this statistical analysis plan (SAP) is to describe the planned analyses and reporting for the Orasis 20-150-0002 protocol, Version 2.0 (Amendment 1), dated 07Jan2021 (NEAR-1 study).

This Version 2.0 SAP replaces the previous finalized and signed Version 1.0 SAP, dated 22Nov2021.

This SAP is being written with due consideration of the recommendations outlined in the most recent International Council for Harmonisation (ICH) E9 Guideline entitled Guidance for Industry: Statistical Principles for Clinical Trials and the most recent ICH E3 Guideline entitled Guidance for Industry: Structure and Content of Clinical Study Reports.

This SAP describes the data that will be analyzed and the subject characteristics, efficacy, and safety assessments that will be evaluated. This SAP provides details of the specific statistical methods that will be used. The statistical analysis methods presented in this document will supersede the statistical analysis methods described in the clinical protocol. Any additional analyses required to supplement the planned analyses described in this SAP will be duly noted in the clinical study report.

2. Study Objectives

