8.5 Adjustment for Multiplicity

If the primary null hypothesis, H_{01} , is rejected at a 2-sided alpha = 0.05 in favor of CSF-1 in the alternative hypothesis, H_{11} , tested as delineated in the primary efficacy analysis section ([Section 12.1](#)), then the study will be considered a success and the following key secondary hypotheses will be tested in hierarchical order, each at a 2-sided alpha = 0.05, where inference will be made on each null hypothesis only if the prior null hypotheses are rejected in favor of CSF-1.

1. Visit 3 (Day 8), 2 hours following Dose 1 (H_{02})
2. Visit 3 (Day 8), 1 hour following Dose 2 (H_{03})
3. Visit 3 (Day 8), 2 hours following Dose 2 (H_{04})

9. Disposition of Subjects

Subject disposition will be presented in terms of the numbers and percentages of subjects who were randomized, completed the study, and discontinued from the study. A discontinued subject is someone who does not complete the 4 protocol-defined study visits. Subjects who are not discontinued from the study will be considered study completers. Disposition will be summarized by treatment arm for all randomized subjects. The reasons for study discontinuation will also be summarized and include: AE, lost to follow-up, physician decision, protocol violation, study terminated by sponsor, withdrawal by subject, death, and other. A subject listing will be provided which includes the date and reason for study discontinuation.

The number of subjects in each of the analysis sets (FAS, PPS, and SAF) will be displayed by treatment arm, with the number of subjects and percentages calculated using randomized subjects as the denominator. The number and percentage of subjects with any (major, or minor) protocol deviations will be summarized by treatment arm and overall for all randomized subjects. Protocol deviations will be classified as major or minor prior to the closure of the database during a masked review of each protocol deviation. Major deviations will be defined as those deviations that potentially affect the analysis of the primary study endpoint.

A subject listing will be provided which includes the date of the deviation, the deviation code and description, and the classification of whether the deviation was deemed major or minor. In addition, subject listings will include treatment arm and ICF signature date, and exclusions from the PPS. There will also be a listing of screen failures.

10. Demographic and Baseline Characteristics

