12.1 Primary and Key Secondary Efficacy Analysis

The primary efficacy endpoint in this study is the percentage of subjects with a ≥ 3 -line (15-letter) gain, from baseline, in best distance-corrected visual acuity (BDCVA) at 40 cm (Precision Vision chart) and no loss in BDCVA ≥ 5 letters (ETDRS chart) at Visit 3, 1 hour following Dose 1 in the study eye. The key secondary efficacy endpoints are defined the same as the primary efficacy endpoint, except for being measured at 2 hours following Dose 1, 1 hour following Dose 2, and 2 hours following Dose 2, all at Visit 3.

The primary and key secondary efficacy analysis will be conducted in the FAS with missing data handled in the following manners:

1. Discontinuation of study drug and non-optimal compliance will be ignored [treatment policy strategy].
2. Withdrawal due to lack of efficacy or AEs: missing data will be singly imputed as failure [hypothetical strategy].
3. Missing data without withdrawal or withdrawal due to reasons other than lack of efficacy or AEs: missing data will be imputed employing Multiple Imputation (MI) using randomized treatment-based Markov Chain Monte Carlo (MCMC) methods.

No subject data will be excluded from the FAS due to protocol violations/deviations. The multiple imputation of missing values will be completed for the continuous measures (BDCVA at 40 cm and BDCVA at 4 m), then the response variable will be determined therefrom. Imputation of failure due to lack of efficacy or AE will be assigned after multiple imputation is performed.

Variables for treatment group, baseline for BDCVA at 40 cm and baseline for BDCVA at 4 m will also be included in the multiple imputation model. 25 complete imputed datasets will be created.

Example SAS® code for the multiple imputation:

```
PROC MI DATA=DATAIN OUT=MI NIMPUTE=25 SEED=118787 minimum=-0.3 maximum=1;
  MCMC INITIAL=EM;
  VAR TRTPN VA40 VA40BL VA4 VA4BL;
RUN;
```

Where TRTPN = treatment group, coded 1 for CSF-1, else 0

VA40 = value of BDCVA at 40 cm for Visit 3, 1 hour after Dose 1

VA40BL = baseline value of BDCVA at 40 cm

VA4 = value of BDCVA at 4 m for Visit 3, 1 hour after Dose 1

VA4BL = baseline value of BDCVA at 4 m

For each imputed dataset, a logistic regression model with baseline BDCVA at 40 cm as a covariate and treatment as a main effect will be used to obtain the treatment effect estimate, odds ratio, and 95% confidence interval (CI) for odds ratio.

Example SAS® code for the logistic model is shown here:

```

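### Does a per-protocol set tied to the Dose 1 primary endpoint leave the post-Dose 2 per-protocol results unsound?

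*SAP*

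**What the plan says.** The two documents define the per-protocol set in nearly the same terms. Protocol 10.3 takes FAS subjects "who do not have significant protocol deviations that affect the primary endpoint analysis", and SAP 7.2 takes those "who do not have significant protocol deviations that affect the primary efficacy endpoint analyses".

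The analysis behind those words differs:

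- **Protocol.** The primary analysis (Synopsis and 10.7) is a mixed model at 1 hour holding both daily doses, with a "random effect of subject to account for the correlation within a subject between daily doses". According to the Synopsis, if the dose-by-treatment interaction is not significant, "testing of treatment effect will be completed within the model pooled over dose".
- **SAP.** Section 12.1 fits a logistic regression with treatment and baseline near acuity only. The example imputation code for the primary endpoint uses the baselines, treatment and the Dose 1 readings, for instance "VA40 = value of BDCVA at 40 cm for Visit 3, 1 hour after Dose 1".

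The SAP Introduction says that its methods "will supersede the statistical analysis methods described in the clinical protocol".

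SAP 7.2 also gives the set a wider role: "The PPS analysis will be supportive of the primary and key secondary efficacy analysis performed with FAS". SAP 12.2, item 3, accordingly runs an observed-data analysis in the PPS for the primary and key secondary endpoints. SAP Section 9 sets the deviation classes: "Major deviations will be defined as those deviations that potentially affect the analysis of the primary study endpoint". It plans counts of any, major and minor deviations by arm, and a listing with date, code, description and class.

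**The concern.** The wording of the definition stayed the same while the analysis it points to became narrower. Under the protocol's two-dose model, a missed or wrong Visit 3 Dose 2, or a faulty reading 1 hour after it, enters the primary test directly and could be a ground for exclusion. Under the SAP, Dose 2 is nominally given two hours after Dose 1, later than the primary reading. A deviation confined to it cannot touch the primary analysis. Read literally, it would be classed as minor and the subject would stay in the PPS.

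Two of the three key secondary endpoints are measured after Dose 2. A reader of the H03 or H04 per-protocol result might assume that subjects with a faulty Dose 2 had been removed when they had not. The masked deviation review, which must finish before database lock, might also hesitate over such a case. At stake is how cleanly a supportive result can be read; the tests of the hypotheses are not involved.

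**Working it through.** **Step 1. Does the reach of the definition change?**

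| | Protocol | SAP |
|---|---|---|
| Primary endpoint | Visit 3, 1 h after Dose 1 | Visit 3, 1 h after Dose 1 |
| Data in the primary model | 1 h after Dose 1 and 1 h after Dose 2 | 1 h after Dose 1 |
| Ground for exclusion | deviation affecting the primary endpoint analysis | same |

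If the ground is read as the model, its reach narrows. If it is read as the endpoint, it does not, because the endpoint and H01 are identical in both documents. Neither document says how a Visit 3 Dose 2 deviation is to be classed, so the narrowing is an inference. For a deviation confined to a 2-hour reading (H02, H04), neither document's 1-hour primary analysis is affected, so nothing changed there.

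**Step 2. Which deviations could matter?** Eligibility failures, prohibited medication and a wrong kit also affect the primary reading, so they can still exclude a subject for every endpoint. A subject with no reading after Dose 2 drops out of the H03 and H04 per-protocol analyses anyway, because these use observed data only. What is left is a deviation confined to the period after the primary reading in a subject who still has a recorded value. Dose 2 at Visit 3 is instilled by study staff.

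**Step 3. The plan's own figure.** Inputs from SAP Section 5: 140 per arm, 42.5% v 17.5%, Pearson chi-squared, two-sided 0.05.

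- SE under the null = √(2 × 0.30 × 0.70 / 140) = 0.0548
- SE under the alternative = √((0.425 × 0.575 + 0.175 × 0.825) / 140) = 0.0527
- Power = Φ((0.25 − 1.96 × 0.0548) / 0.0527) = 99.66%, which agrees with the stated >97.5%

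**Step 4. Bounds on the H03 per-protocol difference.** Section 5 applies these rates 1 hour after each dose, so they cover H03; using them for H04 is an assumption. So is a PPS of 140 per arm. Expected responders are 0.425 × 140 = 59.5 and 0.175 × 140 = 24.5, a difference of 25.0 points (z = 0.25 / 0.0548 = 4.56). Let k subjects per arm be in or out depending on how the definition is read.

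- Lowest (all k in the CSF-1 arm are responders, all k in the Vehicle arm are non-responders): (59.5 − k − 24.5) / (140 − k)
- Highest (the reverse): (59.5 − 24.5 + k) / (140 − k)

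| k per arm | Lowest | Highest |
|---|---|---|
| 3 (2.1%) | 32/137 = 23.4 points | 38/137 = 27.7 points |
| 7 (5%) | 28/133 = 21.1 points | 42/133 = 31.6 points |

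For the lowest case at k = 7, the pooled rate is 77/266 = 0.289, the SE is √(2 × 0.289 × 0.711 / 133) = 0.0556, z = 3.79 and p ≈ 0.00015.

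**Step 5. A less extreme case.** Suppose a share f of the CSF-1 arm has a Dose 2 deviation, stays in the set and responds at the Vehicle rate. The difference becomes 25.0 × (1 − f).

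| f | Difference if kept | Power, 140 per arm | Power if the share f of each arm is removed (25.0 points) |
|---|---|---|---|
| 2% | 24.5 | 99.6% | 99.6% (137 per arm) |
| 5% | 23.75 | 99.4% | 99.5% (133 per arm) |
| 10% | 22.5 | 98.8% | 99.3% (126 per arm) |
| 20% | 20.0 | 96.7% | 98.6% (112 per arm) |

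Up to 10%, keeping or removing these subjects changes power by no more than half a percentage point.

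**The case for a change.** The best case for acting is that the fix is nearly free and the moment for it is before lock. The term for a significant deviation is not defined in the readable text, the classification has to be settled while masked, and the protocol's two-dose model and the SAP's single-dose model can be read to give different answers for the same event. One sentence in SAP 7.2 and one count drawn from data already planned for the listing would settle it. The H03 and H04 per-protocol results could then be read without guessing who was kept.

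Part of this stands. On a literal reading the set does not screen for Dose 2 deviations, and the readable text shows no separate tabulation of them. The rest carries less weight:

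- The SAP says its methods override the protocol's, and Section 9 ties the major class to the primary endpoint, so the deviation review has one operative rule.
- Dose 2 deviations are already inside the planned by-arm counts of any, major and minor deviations, and the listing identifies them.
- The contents of SAP Sections 16 (changes from the protocol), 18 (revision history) and 19 (tables) are not visible in the copy available. It cannot be said that the change in model or such a table is missing.
- Endpoint-specific per-protocol sets would bring selection on post-randomisation events, a worse problem than the one they would solve.

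**Conclusion.** No change is needed. The observation is right as far as it goes: the SAP anchors one PPS and its major-deviation class on an endpoint read 1 hour after Dose 1, and uses that set to support H02 to H04 as well. This is an ordinary trade-off. A single set, fixed before unmasking, gives up some fit to the later endpoints and avoids further post-randomisation selection. The unstated detail is one that a masked review settles sensibly under the SAP's rule.

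The actual size cannot be known, because no deviation rate is given and the assessment windows are redacted. Under the stated assumptions (the plan's response rates, 140 per arm, up to 5% of each arm affected), the per-protocol difference stays between 21.1 and 31.6 points and the conclusion holds throughout. The analyses concerned are supportive, and the FAS tests of all four hypotheses are untouched. A sentence on the anchoring, or a footnote counting retained subjects with a later deviation, would be an optional courtesy to the reader of the report. It would alter no analysis set, test or conclusion.
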